8.2.2.2.1. Inclusion Criteria for Ad26.COV2.S Exposed Cohort

To enter the exposed cohort individuals must satisfy ALL of the following criteria at the reference date:

- 1. Have at least 1 year of continuous health plan enrollment with medical and prescription drug coverage prior to the reference date with a required length of the longer of the following periods:
 - a. At least 1 year before the reference date
 - b. An earliest coverage date on or before 11 December 2020 (to maximize ability to identify the first COVID-19 vaccine administered during the study period)
- 2. Receive 1 dose of Ad26.COV2.S on the reference date

The reference date for this cohort will be the date of the first dose of Ad26.COV2.S. The exit rules for this cohort are listed in Section 8.3.5.2.

8.2.2.2. Inclusion Criteria for Concurrent Active Comparator Cohort

To enter the active comparator cohort, individuals must:

- 1. Have continuous health plan enrollment with medical and prescription drug coverage prior to the reference date with a required length of the longer of the following periods:
 - a. At least 1 year before the reference date; days
 - b. An earliest coverage date on or before 11 December 2020 (to maximize ability to identify the first COVID-19 vaccine administered during the study period)
- 2. Receive the first dose of the primary series of BNT162b2 on the reference date.

The exit rules for this cohort are listed in Section 8.3.5.2.

8.2.2.2.3. Exclusion Criteria for Exposed and Active Comparator Cohorts

Individuals will be excluded from the exposed and active comparator cohorts if:

- 1. They have been vaccinated with any COVID-19 vaccines at any time prior to the reference date.
- 2. They had records of more than 1 COVID-19 vaccine brand on the reference date.
- 3. They are aged < 18 years on the reference date.

Individuals with diagnosis of any of the AESIs in the AESI-specific washout periods prior to the reference date (Section 8.3.4.2) will not be excluded from the overall study population. However, individuals with diagnoses of AESIs in outcome-specific washout periods before the reference date will be excluded from outcome-specific analyses of those AESIs. Washout periods for each AESI are defined in Table 1.

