8.3.2. Individual Characteristics

Population characteristics will be identified based on medical, pharmacy and procedure codes, and insurance enrollment information. The following variables will be used to characterize the study population and will be included in PS models for the cohort design (as described in Section 8.7.2.1):

- Demographic characteristics (at reference date) such as age, sex, race/ethnicity (if feasible, as determined during the monitoring phase of the study), and a proxy for SES, if feasible, calculated using geographic information at least as granular as a patient's 5-digit ZIP code and geographic area (eg, state, or census region)
- Pregnancy status (at reference date)
- Indicators of frailty
 - Frailty will be assessed using an index developed by Kim et al. (Kim 2019) To calculate the frailty index, relevant diagnosis and procedure codes will be identified in the 365 days before day 0 (including day 0). Each variable will be assigned variable-specific weights, and the weights will be summed. Cutoff points will be defined in the SAP.
- 1-year medical history (at reference date)
 - Comorbidities such as cancer, chronic kidney disease, heart conditions, COPD, asthma, sickle cell disease, immunocompromised states, obesity, Down syndrome, Type 2 diabetes
 - Healthcare utilization eg, mean number of emergency department visits, inpatient visits
 - Medication use (eg, drug class utilization)
 - Previous history of COVID-19 infection (evidence of either of the following)
 - O Diagnosis codes for COVID-19 (yes/no)
 - O SARS-CoV-2 positive laboratory result from NAAT, antigen, or serology tests if available (evidence of a positive test, yes/no)
- The ability to identify SARS-CoV-2 positive tests may be limited due to incomplete capture of test results in the Sentinel data sources. Currently, some Data Partners are in the process of incorporating NAAT and antigen tests and results into the data sources. SARS-CoV-2 serology tests and results are not yet available but if captured in the data sources may be provided in the future. The extent of availability of relevant laboratory test results in the Sentinel sites participating in this study will be evaluated during the monitoring phase.

Vaccinations:

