8.3.4.2. Risk Windows

Status: Approved, Date: 20 October 2022

Table 1: AESI-Specific Risk Windows and Background Incidence Rates

Body system	AESI	Disease-specific washout period before administration of Ad26.COV2.S or BNT162b2 for active comparator design	Disease- specific washout period before event for SCRI design	Disease- specific risk period following the administration of Ad26.COV2.S or BNT162b2	Range of adult background rates per 100,000 person- years reported in the external literature ^{a,b}
Nervous and central nervous system	Encephalitis, including ADEM & meningoencephalitis	180 days	180 days	1-42 days	2-73 (Li X et al. 2021; Baker MA et al. 2013; Ostropolets A et al. 2022; Esposito D et al. 2018)
	Guillain-Barré Syndrome	365 days	365 days	1-42 days	< 1-23 (Baker MA et al. 2013; Li X et al. 2021; Klein NP et al. 2010; Ostropolets A et al. 2022; Esposito D et al. 2018)
	Transverse myelitis	365 days	365 days	1-42 days	< 1-5 (Baker MA et al. 2013; Li X et al. 2021; Klein NP et al. 2010; Ostropolets A et al. 2022)
	Bell's palsy	180 days	180 days	1-42 days	40-174 (Li X et al. 2021; Baker MA et al. 2013; Ostropolets A et al. 2022)
	Multiple sclerosis, including optic neuritis	All available	Not applicable for SCRI	1-365 days	2-29 (Alonso A and Hernán MA 2008; Klein NP et al. 2010; Esposito D et al. 2018)
	Sensorineural Hearing loss	365 days	365 days	1-21 days	12-81 (Alexander TH and Harris JP 2013)
	Generalized convulsions (without epilepsy)	180 days	180 days	1-14 days	25-120 (Kotsopoulos I et al. 2005)
	Generalized convulsions (with epilepsy)	365 days	365 days	1-14 days	14-62 (Kotsopoulos I et al. 2005)

CONFIDENTIAL – FOIA Exemptions Apply in U.S.

Body system	AESI	Disease-specific washout period before administration of Ad26.COV2.S or BNT162b2 for active comparator design	Disease- specific washout period before event for SCRI design	Disease- specific risk period following the administration of Ad26.COV2.S or BNT162b2	Range of adult background rates per 100,000 person- years reported in the external literature ^{a,b}
Immune system	Autoimmune thyroiditis	All available	Not applicable for SCRI	1-365 days	5-97 (Klein NP et al. 2010; Esposito D et al. 2018)
	Immune thrombocytopenia	365 days	365 days	1-42 days	1-56 (Baker MA et al. 2013; Klein NP et al. 2010; Li X et al. 2021; Ostropolets A et al. 2022; Esposito D et al. 2018)
	Thrombocytopenia	90 days	90 days	1-42 days	

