	Type 1 diabetes mellitus	All available	Not applicable for SCRI	1-365 days	19-382 (Klein NP et al. 2010; Baker MA et al. 2013; Esposito D et al. 2018)
	Acute aseptic arthritis ^c	All available	Not applicable for SCRI	1-365 days	3-205 (Pennisi M et al. 2019; Esposito D et al. 2018)
	Anaphylaxis	180 days	180 days	0-2 days	7-85 (Lee S et al. 2017; Baker MA et al. 2013; Li X et al. 2021; Ostropolets A et al. 2022; Esposito D et al. 2018)
	Composite endpoint – Cardiac inflammatory disorders, including myocarditis and pericarditis	365 days	365 days	1-21 days	2-54 (Li X et al. 2021; Baker MA et al. 2013; Ostropolets A et al. 2022)
	Microangiopathy	365 days	365 days	1-28 days	
	Heart failure	All available	All available	1-28 days	812-5,020 (Cuthbertson CC et al. 2018) ^d
	Stress cardiomyopathy	365 days	365 days	1-28 days	
	Coronary artery disease, including acute myocardial infarction	All available	All available	1-28 days	41-823 (Manemann 2015)
	Acute myocardial infarction	180 days	180 days	1-28 days	6-1,514 (Li X et al. 2021; Ostropolets A et al. 2022)
	Arrhythmia	All available	All available	1-14 days	9-6,195 (Kjerpeseth LJ et al. 2021) ^e

CONFIDENTIAL – FOIA Exemptions Apply in U.S. Status: Approved, Date: 20 October 2022

Body system	AESI	Disease-specific washout period before administration of Ad26.COV2.S or BNT162b2 for active comparator design	Disease- specific washout period before event for SCRI design	Disease- specific risk period following the administration of Ad26.COV2.S or BNT162b2	Range of adult background rates per 100,000 person- years reported in the external literature ^{a,b}
Blood and lymphatic system	Deep vein thrombosis	180 days	180 days	1-28 days	66-1,206 (Li X et al. 2021; Huang W et al. 2014; Ostropolets A et al. 2022)
disorders	Pulmonary embolism	180 days	180 days	1-28 days	20-427 (Li X et al. 2021; Huang W et al. 2014; Ostropolets A et al. 2022)
	Disseminated intravascular coagulation	180 days	180 days	1-28 days	< 1-203 (Li X et al. 2021; Singh B et al. 2013; Ostropolets A et al. 2022)
	Non-hemorrhagic stroke	180 days	180 days	1-28 days	17-1,523 (Li X et al. 2021; Feigin VL et al. 2015; Ostropolets A et al. 2022)
	Hemorrhagic Stroke	180 days	180 days	1-28 days	13-506 (Li X et al. 2021; Feigin VL et al. 2015; Ostropolets A et al. 2022)
	Cerebral venous thrombosis	180 days	180 days	1-28 days	< 1-1.7 (Coutinho JM et al. 2012)
	Peripheral arterial thrombosis	180 days	180 days	1-28 days	, , , , , , , , , , , , , , , , , , ,

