8.3.5.2. Cohort Design with Concurrent Active Comparator

Follow-up time for the primary objective evaluating the first dose of Ad26.COV2.S or the primary series of BNT162b2 will start on or the day after the reference date (depending on the specific AESI risk window) and will continue until the earliest of the following:

- date of first diagnosis of the AESI
- end of the duration of the disease-specific risk period (specified in Table 1; up to 1 year after the reference date)
- disenrollment from the health plan
- administrative end of study (eg, end of available data)
- death
- date of any COVID-19 vaccine that is a different brand than the index vaccine
- date of receipt of an additional or booster dose beyond the authorized primary series (ie, a second dose of COVID-19 vaccine in the Ad26.COV2.S cohort or a third dose of COVID-19 vaccine in the BNT162b2 cohort)

The authorized primary series of BNT162b2 consist of 2 doses, spaced 21 days apart. If the AESI-specific risk period after dose 1 of BNT162b2 ends before a second dose is received, follow-up will end at the end of the dose 1 disease-specific risk period. However, a second dose of BNT162b2 may be received during the dose 1 disease-specific risk periods of some AESI. If a second dose is received before the end of the AESI-specific risk period, the risk periods of dose 1 and dose 2 will be concatenated into a single risk period, and follow-up will end after the duration of the disease-specific risk period following dose 2. To address differential lengths of follow-up time between the exposed and comparator cohorts that will arise from including second doses of BNT162b2 in the comparator cohort, modifications of this criteria will be evaluated in sensitivity analyses (Section 8.7.5).

Note that follow-up time will not be censored if a diagnosis of COVID-19 occurs after the initial vaccine dose. Only severe COVID-19 that arises to medical attention will be captured given the nature of the available data. This information will be captured and used in descriptive analyses.

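### In the cohort design the vaccination day lies in neither the washout nor the risk window for 33 of 34 AESIs, so a diagnosis first coded that day can reappear as an incident event

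*Protocol*

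**What the plan says.** Section 8.2.2.2.3 sets the cohort exclusion: "individuals with diagnoses of AESIs in outcome-specific washout periods before the reference date will be excluded from outcome-specific analyses of those AESIs". It adds "Washout periods for each AESI are defined in Table 1", so the lengths are fixed in the protocol and not left to the SAP. The Table 1 column for this design is headed "Disease-specific washout period before administration of Ad26.COV2.S or BNT162b2 for active comparator design".

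The reference date is the day of the dose. For the exposed cohort, "The reference date for this cohort will be the date of the first dose of Ad26.COV2.S" (Section 8.2.2.2.1); for the comparator it is the day of the first BNT162b2 dose (Section 8.2.2.2). Under Section 8.3.5.2, follow-up "will start on or the day after the reference date (depending on the specific AESI risk window". It ends, among other reasons, at the first diagnosis of the AESI.

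Two Table 1 rows show the contrast: "Anaphylaxis 180 days 180 days 0-2 days" and "Type 1 diabetes mellitus All available Not applicable for SCRI 1-365 days". The anaphylaxis window includes day 0; the type 1 diabetes window, like all the others, does not.

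Two other look-backs are anchored differently. The frailty index uses codes "in the 365 days before day 0 (including day 0" (Section 8.3.2). The SCRI washout in Table 1 and Section 8.2.2.1 is counted back from the event. The prior-AESI indicators for the propensity score (Section 8.3.2) again stop before the reference date.

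**The concern.** The list of definitions gives the purpose of a washout as identifying incident cases more plausibly. A washout that closes on day -1, followed by a window that opens on day 1, leaves one day unassigned. It is also the day on which the person is known to have had a health service contact of some kind.

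Take someone whose condition is first coded on day 0. The washout is clean, so the person stays in that AESI's subcohort. Follow-up opens the next day. If a later claim with the same code is taken as the first diagnosis in follow-up, a condition already present at vaccination is counted as a post-vaccination event. The cohort design is primary for the four non-acute AESIs and is the sensitivity design for the acute ones, so this bears on both uses. The SCRI analyses avoid the problem because a washout counted back from the event spans day 0.

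**Working it through.** **Step 1: count the rows.** Table 1 risk windows:

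| Window | AESI rows |
|---|---|
| 0-2 days | 1 (anaphylaxis) |
| 1-14 days | 5 |
| 1-21 days | 2 |
| 1-28 days | 16 |
| 1-42 days | 6 |
| 1-365 days | 4 |
| Total | 34 |

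Rows starting on day 1: 34 - 1 = 33. Four of these are non-acute (multiple sclerosis, autoimmune thyroiditis, type 1 diabetes, acute aseptic arthritis). The other 33 - 4 = 29 are acute.

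**Step 2: place day 0.** The washout closes before the reference date and the window opens the day after it. No section of the protocol assigns day 0 for these 33 rows.

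**Step 3: ceiling on spurious events.** The protocol gives no figure for day-0 coding, so two assumptions are needed. First codes on day 0 occur at *k* times the average daily background rate, and all of them are re-coded inside the window. For a window of *W* days, spurious events as a share of background events are then *k/W*.

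| W (days) | k = 0.5 | k = 1 | k = 5 |
|---|---|---|---|
| 14 | 3.6% | 1/14 = 7.1% | 5/14 = 36% |
| 21 | 2.4% | 1/21 = 4.8% | 5/21 = 24% |
| 28 | 1.8% | 1/28 = 3.6% | 5/28 = 18% |
| 42 | 1.2% | 1/42 = 2.4% | 5/42 = 12% |
| 365 | 0.14% | 1/365 = 0.27% | 5/365 = 1.4% |

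**Step 4: effect on the rate ratio, equal windows and equal k.** With a true IRR of 2.0 the expected estimate is (2W + k)/(W + k).

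| W (days) | k = 1 | k = 5 |
|---|---|---|
| 14 | 29/15 = 1.93 | 33/19 = 1.74 |
| 28 | 57/29 = 1.97 | 61/33 = 1.85 |
| 42 | 85/43 = 1.98 | 89/47 = 1.89 |
| 365 | 731/366 = 1.997 | 735/370 = 1.99 |

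**Step 5: unequal windows.** Section 8.3.5.2 joins the dose 1 and dose 2 risk periods of BNT162b2 when dose 2 falls inside the dose 1 period. Assume every comparator receives dose 2 on day 21. A 28-day window becomes 21 + 28 = 49 days and a 42-day window becomes 21 + 42 = 63 days, in the comparator arm only. The same carry-over is then spread over more comparator person-time. With a true IRR of 1.0 the expected estimate is (1 + k/W₁)/(1 + k/W₂), where W₁ is the Ad26.COV2.S window and W₂ the BNT162b2 window:

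- 28 against 49 days: (1 + 1/28)/(1 + 1/49) = 1.015 at k = 1; (1 + 5/28)/(1 + 5/49) = 1.07 at k = 5.
- 42 against 63 days: (1 + 1/42)/(1 + 1/63) = 1.008 at k = 1; (1 + 5/42)/(1 + 5/63) = 1.04 at k = 5.

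A null effect can therefore be pushed above 1 even when day-0 coding is the same in both arms.

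**The case against.** **The counting of the repeat code is not in the text.** Section 8.3.5.2 speaks of the first diagnosis. A person first coded on day 0 arguably has that diagnosis on day 0, outside the window, and the next claim is not a first one. A reader might infer that repeat claims will certainly be counted; the protocol does not say so. The counter-argument is that many washouts are only 90 or 180 days, so for those AESIs the first diagnosis cannot mean first ever and must mean first in follow-up. That argument is weakest for the four AESIs where the cohort design is primary, because their washout uses all available history. This part of the objection stands: the gap is in the text, and its consequence is an inference.

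**The primary effect is negligible.** This also stands. A reader might infer that the primary cohort results are materially contaminated, but the 365-day rows above show otherwise. The larger shares belong to acute AESIs, where the cohort design is only a sensitivity analysis.

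**The figures are ceilings.** Section 8.3.3 allows algorithms limited to certain care settings, so a later outpatient code may not qualify. Section 8.3.1 also takes exposure from pharmacy and registry records, so vaccination need not coincide with a diagnostic visit. The protocol itself raises healthy-vaccinee bias, which makes k below 1 plausible. All of this stands.

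**The frailty wording cuts both ways.** One could read its explicit inclusion of day 0 as proof that the AESI washout omits that day on purpose. It could equally show that the authors' word for before is loose, and Section 8.1.1.2 has covariates assessed up to the reference date. The contrast shows that the edge is unstated, not that it was deliberate.

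**The SAP could settle it.** A SAP or event algorithm that treats day-0 codes as prevalent would close the gap. However, the protocol fixes both edges itself and, unlike the SCRI control periods, does not defer this one.

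**Conclusion.** The point holds as a boundary gap with a limited effect. Following both stated edges keeps a person first coded on day 0 at risk, for 33 of 34 AESIs, and allows a repeat code to count as incident unless the event algorithm prevents it.

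For the four primary cohort AESIs the ceiling is about 0.3% of background events at k = 1 and 1.4% at k = 5, which moves a true IRR of 2.0 to 1.997 or 1.99. For the 29 acute AESIs with day-1 windows it is 7.1% down to 2.4% at k = 1, in proportion to k, and only in the cohort sensitivity analysis. Anaphylaxis, the thirtieth acute AESI, is not affected, and neither are the SCRI primary analyses.

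These sizes rest on an assumed k, which could lie below or above 1, and on every day-0 code recurring within the window. It is tempting to conclude that the bias always runs toward 1. That requires equal windows and equal contamination. Where concatenation lengthens the BNT162b2 window, or day-0 coding differs by vaccine, the IRR can move either way.

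**What to change.** In Table 1 and Section 8.2.2.2.3, state that the cohort-design washout runs through and includes the reference date for every AESI whose risk window starts on day 1. Leave anaphylaxis as it is, with its washout ending on day -1. Bring the prior-AESI indicators in Section 8.3.2 into line with the same rule. Report, by arm and AESI, how many people are excluded for a day-0 code; that count also shows whether day-0 coding differs between the vaccines.

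The cost is a line in the table, a clause in the exclusion text and one program parameter. The downside is that anyone with a same-day code leaves that AESI's analysis, including a person with a true same-day reaction. No event inside a risk window is lost, because day 0 is already outside those windows.

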8.3. Variables

8.3.1. Exposure Assessment

Exposure to the Ad26.COV2.S vaccine and the BNT162b2 vaccine will be identified using procedure or pharmacy dispensing codes (eg, National Drug Code, Current Procedural Terminology code, Healthcare Procedure Coding System codes). Where existing linkages with vaccination registries are available within the appropriate Data Partner research databases the vaccine registry data will also be used to assess exposure.

Given the use of a single booster of Ad26.COV2.S vaccine at least 2 months after completion of the single-dose regimen was not authorized until 20 October 2021, for the time period before 20 October 2021, it is not anticipated that many patients will receive more than 1 dose of Ad26.COV2.S vaccine. However, if some patients have a record of more than 1 dose during the study period prior to October 2021, rules based on the time between dose records (to be defined in the SAP) will be used to distinguish between potential coding errors and potentially additional doses (ie, booster doses). Patients with 2 or more doses of Ad26.COV2.S vaccine will be described (see Section 8.7.2.2) but follow-up and AESIs will only be captured after the first dose for the primary analyses (ie, only the first dose will be eligible to be included as a reference date for the primary exposed cohort; follow-up time for the primary analysis will end on the date individuals receive a booster dose of Ad26.COV2.S or a booster dose of any mRNA COVID-19 vaccine).

Exposure to BNT162b2 will also be identified with procedure, pharmacy, and immunization registry data, as available, similarly to Ad26.COV2.S. BNT162b2 is authorized in the US as a 2-dose primary series with additional doses and booster doses authorized for certain groups. Some procedure codes indicate the dose number of BNT162b2, but other procedure codes and NDC codes do not. The dose number of BNT162b2will be inferred from the observed dose number within the claims.

8.3.2. Individual Characteristics

Population characteristics will be identified based on medical, pharmacy and procedure codes, and insurance enrollment information. The following variables will be used to characterize the study population and will be included in PS models for the cohort design (as described in Section 8.7.2.1):

- Demographic characteristics (at reference date) such as age, sex, race/ethnicity (if feasible, as determined during the monitoring phase of the study), and a proxy for SES, if feasible, calculated using geographic information at least as granular as a patient's 5-digit ZIP code and geographic area (eg, state, or census region)
- Pregnancy status (at reference date)
- Indicators of frailty
 - Frailty will be assessed using an index developed by Kim et al. (Kim 2019) To calculate the frailty index, relevant diagnosis and procedure codes will be identified in the 365 days before day 0 (including day 0). Each variable will be assigned variable-specific weights, and the weights will be summed. Cutoff points will be defined in the SAP.
- 1-year medical history (at reference date)
 - Comorbidities such as cancer, chronic kidney disease, heart conditions, COPD, asthma, sickle cell disease, immunocompromised states, obesity, Down syndrome, Type 2 diabetes
 - Healthcare utilization eg, mean number of emergency department visits, inpatient visits
 - Medication use (eg, drug class utilization)
 - Previous history of COVID-19 infection (evidence of either of the following)
 - O Diagnosis codes for COVID-19 (yes/no)
 - O SARS-CoV-2 positive laboratory result from NAAT, antigen, or serology tests if available (evidence of a positive test, yes/no)
- The ability to identify SARS-CoV-2 positive tests may be limited due to incomplete capture of test results in the Sentinel data sources. Currently, some Data Partners are in the process of incorporating NAAT and antigen tests and results into the data sources. SARS-CoV-2 serology tests and results are not yet available but if captured in the data sources may be provided in the future. The extent of availability of relevant laboratory test results in the Sentinel sites participating in this study will be evaluated during the monitoring phase.

Vaccinations:

- Administration of certain vaccines, such as influenza vaccine, any pneumococcal vaccine, any shingles vaccine, or any human papillomavirus (HPV) vaccine during the year before the reference date (for active comparator design) or from 90 days before the reference date and during the risk and control windows (for SCRI design)
- Other vaccinations received concurrently with the Ad26.COV2.S vaccine or BNT162b2 vaccine
- Indicator variables for previous occurrence of each AESI using all available history before reference date (Table 1).

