4. ABSTRACT

Protocol Title: An Observational Post-Authorization Safety Study to Assess the Safety of Ad26.COV2.S Using Health Insurance Databases in the United States 20 October 2022)

Sponsor's Responsible Epidemiologist: PPD PharmD, MSCE, Associate Director Epidemiology (Main Author)

NOTE: The term "sponsor" used throughout this document refers to the entities listed in the Contact Information page(s), which will be provided separately.

SARS-CoV-2 has spread rapidly and globally since its emergence, causing coronavirus disease-2019 (COVID-19). The World Health Organization (WHO) declared that the outbreak constituted a public health emergency of international concern on 30 January 2020 and declared the outbreak to be a pandemic on 11 March 2020.

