8.7.2. Main Statistical Methods

8.7.2.1. Propensity Score Matching

For the cohort designs, matching on calendar time at vaccination (within 2 weeks) and PS will be used to ensure comparability between individuals exposed to Ad26.COV2.S versus BNT162b2. The PS is the predicted probability of an individual being classified in the exposed cohort versus the comparator cohort, given a set of observed covariates. Propensity scores will be estimated with multivariable logistic regression models with Ad26.COV2.S exposure as the dependent variable and baseline covariates as the independent variables. The baseline covariates used to fit the PS model will be the individual characteristics described in Section 8.3.2 and indicators for occurrence of AESI in the disease-washout period described in Section 8.3.4.2.

This large-scale empirical adjustment strategy should address expected confounders that are recorded in the databases, including demographics and comorbidities associated with AESIs. The study will be subject to the limitation that some confounders may be unmeasured or inadequately represented in claims data, including lifestyle behaviors, such as diet and exercise.

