8.7.3. Stratified Analyses

Analyses within the primary study designs (cohort design with active comparator for non-acute events and SCRI design for acute events) will be stratified by the following clinically relevant subgroups:

- select comorbidities (by the presence or absence of comorbidity)
- frailty
- receipt of other vaccinations concurrently with Ad26.COV2.S
- age ([18-39]; [40-59]; [60-79], [80+])
- prior history of thrombotic events and/or thrombocytopenia
- prior history (ever) of specific event more than a year before start of follow-up
- prior history of COVID-19 infection

For the cohort design with active comparator, the original study population before matching will be divided into these subgroups and the PS matching will be repeated in each of the subgroups to create matched exposed and comparator cohorts within the subgroups. The balance of individual characteristics by exposure group will be re-evaluated within each subgroup, and subgroup-specific incidence rate and incidence rate ratios with 95% CIs will be estimated.

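### Previous COVID-19 is looked for only in the year before vaccination, so older recorded infections are coded as no prior COVID-19 for everyone vaccinated after 11 March 2021

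*Protocol*

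**What the plan says.** Section 8.3.2 has a block headed "1-year medical history (at reference date" that holds comorbidities, healthcare utilization, medication use and the item "Previous history of COVID-19 infection (evidence of either of the following". The evidence accepted is a COVID-19 diagnosis code or a positive laboratory result. The Abstract (Section 4) lists the items in the same order under the same heading. No longer window is given for COVID-19 in either place.

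The variable has two uses:
- **PS.** Section 8.7.2.1 states: "The baseline covariates used to fit the PS model will be the individual characteristics described in Section 8.3.2".
- **Strata.** Section 8.7.3 stratifies the SCRI design (acute events) and the cohort design (non-acute events) by "prior history of COVID-19 infection", with no window of its own.

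Other history variables reach further back. Section 8.3.2 asks for "Indicator variables for previous occurrence of each AESI using all available history before reference date". The stratum next to the COVID-19 one in Section 8.7.3 is "prior history (ever) of specific event more than a year before start of follow-up". Section 8.2.2.2 uses all baseline data for the washout of some chronic conditions.

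On data quality, Section 8.3.2 says that "some Data Partners are in the process of incorporating NAAT and antigen tests and results into the data sources" and that capture of test results may be incomplete. It does not mention the length of the look-back.

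**The concern.** A 1-year window suits a chronic comorbidity, which keeps generating claims. COVID-19 is different: it is usually a single episode, and the disease has a calendar start. A rolling window therefore covers a smaller part of the pandemic at each later vaccination date. Take two people with a COVID-19 claim in April 2020, one vaccinated in March 2021 and the other in July 2021. The first is coded yes and the second no, solely because of the vaccination date.

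The error runs one way. A recorded infection more than a year old is always counted as no prior COVID-19, and nobody is moved wrongly into the yes group. The stake is mainly the COVID-19 stratification, which pools all vaccination dates. The summary of changes records that European regulators asked for this stratification. A lesser stake is adjustment in the cohort design.

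**Working it through.** The protocol states no figure for look-back coverage, so there is nothing to reproduce. The check is date arithmetic on the protocol's own dates.

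**Inputs**
- Pandemic start: 11 March 2020 (Section 4: "declared the outbreak to be a pandemic on 11 March 2020"). Alternative start: 30 January 2020, the emergency declaration in the same section.
- First entry: 27 February 2021 (Section 8.2.1).
- Last entry: end of data, about Q2-Q3 2022 (Section 5, footnote b), taken as 1 April to 30 September 2022.
- Look-back: 365 days (Section 8.3.2).
- Coverage required from 11 December 2020 or earlier, and for at least 1 year (Sections 8.2.2.1 and 8.2.2.2).

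**Step 1: share of pandemic time covered** = min(1, 365 / days from start to vaccination)

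| Vaccination date | Days since 11 March 2020 | Covered |
|---|---|---|
| 27 Feb 2021 | 353 | 100% |
| 15 Apr 2021 | 400 | 91% |
| 30 Jun 2021 | 476 | 77% |
| 20 Oct 2021 | 588 | 62% |
| 11 Mar 2022 | 730 | 50% |
| 5 May 2022 | 785 | 46% |

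At the end of entry, coverage is 365/751 = 48.6% (1 April 2022) to 365/933 = 39.1% (30 September 2022). The stretch below 50% is 5% to 35% of the calendar entry period, depending on when the data end. With 30 January 2020 as the start, coverage is 92.6% at first entry, 70.6% on 30 June 2021 and 58.0% on 20 October 2021.

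**Step 2: rough effect on the strata.** The protocol gives 51,102,357 US cases to 21 December 2021 (Section 6.1), day 650. Assume even accrual: 51,102,357 / 650 = 78,619 per day. Assume also a population N of 250 to 330 million, which the documents do not give. Cases inside a full window are 365 × 78,619 = 28.7 million.
- Share of prior cases missed, i.e. loss from the yes stratum: 111 × 78,619 = 8.7 of 37.4 million (23%) on 30 June 2021; 223 × 78,619 = 17.5 of 46.2 million (38%) on 20 October 2021.
- Share p of the no stratum that is misclassified = missed / (N − 28.7 million): 2.9% to 3.9% on 30 June 2021 and 5.8% to 7.9% on 20 October 2021. Carrying the same accrual on to 5 May 2022, 420 × 78,619 = 33.0 million gives about 11% to 15%.

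**Step 3: dilution of the no stratum.** Suppose the true incidence rate ratios (IRRs) are 2.0 in never-infected and 1.0 in previously infected people, with equal baseline rates. The no stratum then shows 2.0 × (1 − p) + 1.0 × p = 2.0 − p. That is 1.96 to 1.97, then 1.92 to 1.94, then 1.85 to 1.89 at the three dates. If previously infected people have higher baseline rates, the dilution is somewhat larger.

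**Step 4: history already in the data.** On 5 May 2022 the enrollment rule guarantees 510 days of history, of which 365 are used. Using all 510 raises coverage from 46.5% to 510/785 = 65.0%. For entries up to 11 December 2021 the guaranteed minimum is still 1 year, so any gain there depends on each person's actual enrollment.

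**The case against.** The strongest reply is that a fixed 1-year window equals the minimum enrollment required, so everyone is assessed over the same length of time, and that the harm is small. Most of this stands as a limit on size:

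- A reader might infer that the stratification hides effect modification. Step 3 does not support this: a contrast of 2.0 against 1.0 stays visible. Nor are both IRRs pulled together. Nobody is moved wrongly into the yes stratum, so only the no-stratum estimate is diluted.
- A reader might take coverage below half as typical. It applies only after 11 March 2022. Amendment 2 cites low utilization and expects minimal further uptake, and the authorization was restricted on 5 May 2022.
- A reader might infer that the cohort IRRs are biased. Matching within 2 weeks makes the look-back nearly equal between arms. Bias also requires that infection more than a year old differ between vaccine groups after adjustment for the other covariates. The documents show no such difference.
- Coverage is in calendar days, not infections. Section 8.3.2 concedes incomplete test capture, and infections never recorded contaminate the no stratum whatever the window.
- The window for the stratum is inferred, since Section 8.7.3 gives none and the SAP may. As the protocol stands, Section 8.3.2 is its only definition.

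What the reply does not answer is the inconsistency. Equal look-back length was not treated as decisive for AESI history or for the adjacent ever stratum, and equal length is not equal coverage of a disease with a calendar start.

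**Conclusion.** The point holds as a modest, one-way misclassification that is cheap to reduce. As written, any recorded infection more than 365 days before vaccination counts as no prior COVID-19. This can affect every entrant after 11 March 2021. Under even accrual it contaminates the no stratum by about 3% to 8% at the mid- and late-2021 dates checked, and removes about 23% to 38% of prior cases from the smaller yes stratum. Those percentages rest on the assumed accrual and population and on reported rather than claims-recorded cases. True losses are lower if early cases were fewer or less often coded. The number of entrants by date is not given, so an overall figure cannot be computed.

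The unstratified SCRI estimates are unaffected, because each person is their own control. For the cohort design the demonstrated effect is lost adjustment information; bias is possible but not shown.

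**What to change.** In Section 8.3.2 and the Abstract, move previous COVID-19 out of the 1-year block. Define it as any COVID-19 diagnosis code or positive test in all available history before the reference date, as for the AESI indicators. State that this definition serves both the PS and the Section 8.7.3 strata.

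The cost is one wording change in two places and one look-back parameter in the distributed program, with no new data collection. The drawback is that look-back then varies with enrollment: people with short enrollment can still be coded no. Including enrollment length in the PS addresses this for the matched cohort comparison, but does nothing for the definition of the strata or for the SCRI design, which uses no PS. For the strata in both designs, add a check restricted to people enrolled since early 2020, or one that repeats the stratification with the 1-year definition.
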